## **Serious Treatment-Emergent Adverse Event (Serious TEAE)**

A Serious TEAE is any TEAE where the 'Serious' flag has been marked as 'Yes'.

## **TEAE Leading to Permanent Withdrawal of Study Treatment**

A TEAE leading to permanent withdrawal of the Study Treatment is defined as a TEAE where the action taken with study treatment is recorded as "Drug withdrawn".

## **TEAE Leading to Death**

A TEAE leading to death is defined as a TEAE where the outcome is recorded as "Fatal". Date of death is recorded on the 'Study Termination' eCRF page.

## **Severe AE**

An AE is classed as severe if the Severity is recorded as "Severe", or if the severity is missing.

## **Relationship to Study Treatment**

A TEAE is classified as 'Related' to Study Treatment if the relationship to study drug was recorded (on the 'Adverse Events' eCRF page,) as "Unlikely", "Possible", "Probable" or "Definite". An AE is classified as unrelated to study medication if the relationship to study medication was recorded as "Not Related". Adverse events with unknown relationship to Study Treatment are counted as 'Related' to Study Treatment.

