To evaluate the effects of Voltaren Gel on correlates of quality of life	Change from baseline in on Days 7, 14, and 21 
 
• Sleep/alertness: Karolinska Sleepiness Scale assessed 1x/day.
 
• Health-related quality of life: EQ-5D-5L
 

Safety	
To monitor any record adverse events (AEs) during study period.	Number and percent of study subjects reporting AEs or serious AEs (SAEs) while on treatment. 
 
• Treatment Related.
 
• Non-Treatment Related.
 

Exploratory	
To explore the link between Voltaren usage, level of pain relief and functional mobility/quality of life	Correlations between Voltaren usage, pain relief and mobility and quality of life indices throughout the trial.
To evaluate time-to meaningful pain relief after Voltaren Gel use	Elapsed time from Voltaren Gel use to achieving time to meaningful pain relief to end of study.

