### 11.4.2 Assessment of Causality

The causality assessment is one of the criteria used when determining regulatory reporting requirements.

For each AE (serious and non-serious), the investigator (or medically qualified designee) **must** provide an assessment of causality on the AE eCRF page and the SAE form (subject to the classification of the AE). The investigator will also document in the medical notes that he/she has reviewed the AE and assessed causality, where applicable.

Property of Haleon - Confidential

May not be used, divulged, published or otherwise disclosed without the consent of  
 Haleon

Clinical Protocol Template, TMF-187821, v11.0. Parent SOP: **CCI**

A “reasonable possibility” of a relationship conveys that there are facts, evidence, and/or arguments to suggest a causal relationship, rather than a relationship cannot be ruled out. Generally, the facts (evidence) or arguments to suggest a causal relationship should be provided.

The investigator will use clinical judgment to determine the relationship and will also consult the Investigator Brochure (IB), Safety Statement and/or Product Information, for marketed products, in the determination of his/her assessment. Alternative causes, such as underlying disease(s), concomitant therapy, other risk factors, and the temporal relationship of the event to the study product will be considered and investigated.

For each AE/SAE, the investigator must document in the medical notes that he/she has reviewed the AE/SAE and has provided an assessment of causality.

The investigator’s assessment of causality must be provided for all AEs (serious and non-serious); the investigator must record the causal relationship in the eCRF, as appropriate, and report such an assessment in accordance with the SAE reporting requirements if applicable.

There may be situations when an SAE has occurred, and the investigator has minimal information to include in the initial report to Haleon. **However, it is very important that the investigator always make an assessment of causality for every event prior to the initial transmission of the SAE data to Haleon.** The investigator may change his/her opinion of causality in light of follow-up information and send an SAE follow-up report with the updated causality assessment.

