### **13.3.3 Safety Analysis(es)**

All AEs will be coded using MedDRA. AEs will be categorized as related, probable, unlikely, or unrelated by responsible authority prior to database lock. The number of AEs/SAEs and number of subjects with AEs/SAEs will be listed and tabulated.

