## 7.4.8 Safety Variables

### Adverse Events

An adverse event (AE) is defined as “any untoward medical occurrence in a clinical study subject, temporally associated with the use of a study product including any washout or lead-in product (or medical device), whether or not considered related to the study product, including any washout or lead-in product (or medical device)”.

An AE can therefore be any unfavourable and unintended sign (including an abnormal laboratory finding), symptom, or disease (new or exacerbated) temporally associated with the use of a study product including any washout or lead-in product (or medical device).

AE data are collected from the time that informed consent was given for the duration of the trial on the ‘Adverse Events’ eCRF page.

The following information is recorded:

- AE term;
- Start date/time;
- End date/time (or ongoing);
- Severity (“Mild”, “Moderate”, or “Severe”);
- Serious (“Yes”, “No”)
  - if AE is serious:
    - Death (‘No’, ‘Yes’) if yes then also date of death;
    - Life threatening (‘No’, ‘Yes’);
    - Hospitalization (‘No’, ‘Yes’) if yes then also start and end date;
    - Significant Disability (‘No’, ‘Yes’);
    - Congenital Anomaly or Birth Defect (‘No’, ‘Yes’);
    - Other Medically important event (‘No’, ‘Yes’);
- Outcome (“Fatal”, “Not recovered/ not resolved”, “Recovered/ resolved”, “Recovered with sequelae / resolved with sequelae”, “Recovering / resolving”, or “Unknown”);
- Relationship to study drug (“Unknown”, “Not Related”, “Unlikely”, “Possible”, “Probable”, or “Definite”);
- Action taken with study treatment (“Dose not changed”, “Dose increased”, “Dose rate reduced”, “Dose reduced”, “Drug interrupted”, “Drug withdrawn”, “Not applicable”, or “Unknown”);
- Other action taken:
  - None (‘No’, ‘Yes’);
  - Medication prescribed (‘No’, ‘Yes’);
  - Device removed (‘No’, ‘Yes’);
  - Surgery (‘No’, ‘Yes’);
  - Other (‘No’, ‘Yes’);

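### The SAP counts adverse events rated Unlikely as treatment-related; this fits poorly with the protocol's causality standard and is not declared as a change

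*SAP*

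**What the plan says.** The eCRF item "Relationship to study drug" has six levels (SAP 7.4.8, Adverse Events): Unknown, Not Related, Unlikely, Possible, Probable and Definite. Under Relationship to Study Treatment, the SAP classifies a TEAE as Related if it was recorded "as 'Unlikely', 'Possible', 'Probable' or 'Definite". It adds: "Adverse events with unknown relationship to Study Treatment are counted as" Related. On the other side, "An AE is classified as unrelated to study medication if the relationship to study medication was recorded as" Not Related. Five of the six levels are therefore tabulated as Related.

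The protocol bears on this in three places:

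- Section 11.4.2 says that a reasonable possibility needs facts, evidence or arguments in favour of causation, "rather than a relationship cannot be ruled out".
- Section 13.3.3 says "AEs will be categorized as related, probable, unlikely, or unrelated by responsible authority prior to database lock". It does not say how these four categories become two.
- Table 3-1 gives the safety endpoint as "Number and percent of study subjects reporting AEs or serious AEs (SAEs) while on treatment", broken down into treatment-related and non-treatment-related.

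The SAP reports the number of subjects with a related TEAE in the AE overview (10.7.1.1) and has a separate table of related TEAEs by SOC and PT (10.7.1.2). SAP 3.5, which lists changes from the protocol, names only the mITT definition.

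**The concern.** An investigator who records Unlikely has considered the event and judged that a causal link is improbable, though not excluded. Counting that event as Related applies a cannot-be-excluded standard, and protocol 11.4.2 contrasts its own standard with exactly that.

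The related/non-related breakdown matters more here than in a controlled trial. The study is single-arm, so no comparator rate separates background events from reactions to the gel, and the investigator's causality rating is the main means of doing so. Protocol 11.1 also defines adverse events broadly: exacerbations of pre-existing conditions and lack of efficacy both count. The subjects are aged 40 to 85 and may use other analgesics. Incidental events rated Unlikely are plausible, and under the SAP rule they would appear in the Related TEAE table beside events the investigator did attribute to the product.

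**Working it through.** The documents give no AE rate by causality category, so there is no planned figure to reproduce. The check compares definitions.

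**Step 1: the two groupings.**

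- SAP rule: Related = {Unlikely, Possible, Probable, Definite, Unknown}; unrelated = {Not Related}.
- Grouping in line with protocol 11.4.2, keeping the SAP's rule for Unknown: Related = {Possible, Probable, Definite, Unknown}; unrelated = {Not Related, Unlikely}.

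The sets differ by one level, Unlikely.

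**Step 2: direction.** The second Related set lies inside the first, so the SAP count can never be lower.

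- Subjects: the excess is the number of subjects with at least one Unlikely TEAE and no TEAE rated Possible, Probable, Definite or Unknown. If there are none, the subject count does not change.
- Events: SAP 10.7.1.2 also tabulates per event, and there the excess is every Unlikely TEAE.

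**Step 3: size, on assumed rates only.** Let p be the share of subjects with at least one TEAE rated Possible, Probable, Definite or Unknown, and u the share with at least one rated Unlikely. If the two are independent, the share called Related under the SAP is 1 − (1 − p)(1 − u), and its ratio to p is 1 + u(1 − p)/p. No value of p or u comes from the documents.

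| Assumed p | u = 0 | u = 2% | u = 5% | u = 10% |
|---|---|---|---|---|
| 2% | 2% | 3.96% | 6.9% | 11.8% |
| 5% | 5% | 6.9% | 9.75% | 14.5% |
| 10% | 10% | 11.8% | 14.5% | 19% |

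At p = 2% and u = 10% the ratio is 1 + 0.10 × 0.98/0.02 = 5.9. At p = 10% and u = 2% it is 1 + 0.02 × 0.90/0.10 = 1.18. At u = 0 it is 1.0. Scaled to the planned enrolment of 195, these cases are 3.9 against 23.0 subjects, 19.5 against 23.0, and no change. The excess is smaller if the same subjects tend to report both kinds of event. The table shows only that the effect may be nil or may dominate a small related count.

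**Step 4: the scales.** Protocol 13.3.3 has four categories: related, probable, unlikely and unrelated. The eCRF has six. Possible, Definite and Unknown have no counterpart by name in the protocol's list, and neither document maps one scale to the other.

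**The case against.** The strongest reply is that the protocol never defines related for the tables. Section 11.4.2 guides the investigator's assessment and is introduced in connection with regulatory reporting. It does not mention Unlikely, and the eCRF scale does not use the phrase reasonable possibility. Section 13.3.3 keeps unlikely apart from unrelated as well as from related, so a two-way split has to place it on one side without instruction. This stands. A reader might infer that the SAP breaks an explicit protocol definition. The documents do not support that; the tension comes from reading 11.4.2 and 13.3.3 together.

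The rule also fits the SAP's cautious handling of safety data: partial dates are imputed to the worst case, missing severity counts as severe, and Unknown causality counts as Related. That stands in part. Those rules deal with information that is absent, whereas Unlikely is a judgement that was made.

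Finally, the AE listing (SAP 10.7.1.3) shows raw and derived data, so a reader could regroup by hand. The overview is not limited to the items named, and the table shells are in a separate document. A display by category therefore cannot be assumed absent, although SAP section 10.7 does not name one.

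**Conclusion.** The point holds as a mismatch that should be resolved or declared. The SAP's two-way split rests on a wider standard than the one protocol 11.4.2 describes, and SAP 3.5 is silent about it. Only the direction is certain: the related count is equal or higher, and the unrelated count equal or lower, than under the protocol's standard. The documents give no basis for a size, and the ratios of 1.0 to 5.9 in the working rest wholly on assumed rates.

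Two stronger inferences should be resisted. One is that the related rate will be inflated by some stated amount; it may not change at all. The other is that the safety results as a whole are compromised. The rule errs only towards over-counting, so it removes no event from the related count. No safety hypothesis is tested. What is affected is the clarity of the related/non-related breakdown, within an endpoint that otherwise counts subjects with any AE or SAE.

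**What to change.** In SAP 7.4.8, define Related as Possible, Probable or Definite, plus Unknown or missing, and define not related as Not Related or Unlikely. Add one table of subjects with TEAEs by each recorded causality category, so that any reader can rebuild the wider grouping. State how the four categories in protocol 13.3.3 correspond to the six eCRF levels.

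If the sponsor prefers the present grouping, list it in SAP 3.5 with a reason and still add the table.

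The cost is a short SAP edit and one small table, with no new data collection. The drawback is a less conservative headline count of related events, which the category table offsets.

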## **Urine Pregnancy**

Urine pregnancy data are recorded at screening and Day 21 on the "Urine Pregnancy Test" eCRF page for female subjects. The following variables are collected:

- Childbearing potential ("Yes", "No")
- Test performed ("Yes", "No")
  - Reason if not performed
- Date of Test
- Result ("Negative", "Positive")

## 8. Analysis Methods

### 8.1 General Methods

Post-Text TLFs are provided in collated electronic PDF files.

For continuous variables, the mean, standard deviation, minimum, median and maximum are presented, together with the total number of observations and the number of missing and non-missing values. Unless otherwise specified, minimum and maximum values are reported to the same number of decimal places as the recorded measurements; mean and median are reported to one more decimal place and standard deviation one additional decimal place more than the mean.

For categorical variables, absolute and relative frequencies are reported. Relative frequencies are based on all observations and reported as percentages to one decimal place. Unless otherwise specified, percentages are based on the number of subjects with data and are not calculated for missing categories.

Adverse events are reported on a per-subject basis, i.e. if a subject reported several events coded to the same coding term the subject is counted only once at the respective level of display. The percentages are calculated using the number of subjects in the population Analysis Set as the denominator.

All hypotheses are tested at a 5% level of significance using a two-sided test unless otherwise specified.

P-values are rounded to three decimal places. If a p-value is less than 0.001 it is reported as "<0.001." If a p-value is greater than 0.999 it is reported as ">0.999.

### 8.2 Specific Methods for Efficacy Analyses

For the primary and secondary endpoints where the data is collected through the activity tracker, only subjects who meet the minimum wear threshold will be included in the analysis. This is defined as a minimum of 3 valid days during the baseline period and a minimum of 3 valid days within each post-baseline 7-day period, where a valid day is defined as a minimum wear of 20 hours per day.

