### 13.3.1 Primary Analysis

Total study duration is 28 days, with primary analysis performed post baseline (baseline is from Day -7 to Day 0). For primary analysis, average minutes of MVPA on Day 7 will be calculated over all non-missing days between study day 1 (product usage) through 7, inclusive.

Average minutes of MVPA on Day 14 will be calculated over all non-missing days between study day 8 through 14, inclusive. Average minutes of MVPA on Day 21 will be calculated over all non-missing days between study day 15 through 21, inclusive. Any days beyond day 21 will be excluded from all summaries and analyses and will only be present in listed data.

A Mixed Model with Repeated Measures (MMRM) will be used to analyse the change from baseline in MVPA average minutes as the response variable. Subjects will be included as a random effect, and timepoint will be treated as a repeated measure within each subject. If data are found to be non-normal, an appropriate non-parametric test will be performed. If the parameter for the intercept (with compound symmetry structure between visits) is found to be statistically significant ( $p\text{-value} < 0.05$ ), then the individual timepoints (with unstructured covariance structure between visits) will be added as a fixed effect and adjusted means for each timepoint will be presented. P-values and 95% confidence intervals (CIs) for the mean change from baseline in MVPA will be obtained and presented for each timepoint. Other than the global test for an overall change from baseline (i.e., intercept), there will be no other adjustment for multiplicity.

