### **3.5 Changes in the Conduct of Study or Planned Analysis compared to protocol**

Protocol Version Final 4.0 dated 08JUL2024 states in Section 13.2 on page 55 that:

“The modified Intent-To-Treat (mITT) population will include all subjects who use study product at least once and have data from at least one post baseline QoL questionnaire to support at least one of the secondary endpoint assessments. QoL and ePRO data will be summarized using the mITT population only”.

This has been updated in the SAP to include that subjects must meet the inclusion/exclusion criteria to be included in the mITT as below:

“The modified Intent-To-Treat (mITT) population will include all subjects who meet the inclusion/exclusion criteria, who use study product at least once and have data from at least one post baseline QoL questionnaire to support at least one of the secondary endpoint assessments (i.e. have a non-missing response in the ‘Western Ontario and McMaster University Osteoarthritis Index’ or ‘EQ-5D-5L Quality of Life Questionnaire’ eDiary pages). The mITT population will be used for all efficacy analysis.”

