#### Modified Intent-To-Treat (mITT) population

The modified Intent-To-Treat (mITT) population will include all subjects who meet the inclusion/exclusion criteria, who use study product at least once and have data from at least one post baseline QoL questionnaire to support at least one of the secondary endpoint assessments (i.e. have a non-missing response in the 'Western Ontario and McMaster University Osteoarthritis Index' or 'EQ-5D-5L Quality of Life Questionnaire' eDiary pages). The mITT population will be used for all efficacy analysis.

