#### 8.2.2 Primary Analysis

The primary efficacy endpoint is the average MVPA at Days 7, 14 and 21 as detailed in section 7.4.7.1.

The primary analysis will follow a hierarchical approach as follows:

1. A Mixed Model with Repeated Measures (MMRM) is used to analyse the change from baseline in MVPA average minutes as the response variable with baseline as a fixed effect. Subjects will be included as a random effect, and timepoint will be treated as a

repeated measure within each subject (with compound symmetry structure between visits). If the parameter for the intercept is found to be statistically significant (p-value < 0.05), then the second model below will be used.

2. A Mixed Model with Repeated Measures (MMRM) is used to analyse the change from baseline in MVPA average minutes as the response variable with baseline and timepoint (with unstructured covariance structure between visits) as fixed effects. Adjusted means for each timepoint will be presented along with p-values and 95% confidence intervals (CIs) for the mean change from baseline in MVPA.

Other than the global test for an overall change from baseline (i.e., intercept), there will be no other adjustment for multiplicity. If data are found to be non-normal, the Friedman Test will be used. If the Friedman test is found to be significant then Wilcoxon Signed Rank Pairwise Tests are used for each week comparison.

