### 8.2.5 Statistical/Analytical Issues

#### 8.2.5.1 Handling of Dropouts or Missing Data

In the derivation of endpoints there is no replacement of missing data except for adverse event dates as detailed in section 7.2.2.

The primary and secondary analysis method employs mixed-model with repeated measures analysis techniques which use information from the observed data, likelihood-based estimation, subject-specific effects and the within-subject correlation structure to provide information about the unobserved data (although missing data are not explicitly imputed). This analysis uses the available data to provide information about the unobserved data and estimates the treatment effects assuming the withdrawn subjects has the same statistical behaviour as those who continue. Data is not imputed for this type of analysis.

Missing data due to general dropout/withdrawals will be assessed on an ongoing basis during the study. Any further sensitivity analyses needed due to missing data will be reviewed at the time of data review.

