## 10.3 Data Sets Analysed

The number of subjects in each Analysis Set defined in Section 6.1 is summarized by absolute counts (n) and percentages (%), by treatment and overall, for the Enrolled Population in Table CCI.

Listing CCI presents the inclusion into each Subject Analysis Set defined in 'Section 6.1', including the primary reason for exclusion from the SAF and mITT, for the Enrolled Population.

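### The 20-hour wear rule removes whole subjects, so one short week takes their valid weeks out of the primary analysis

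*SAP*

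**What the plan says.** SAP 8.2 restricts the primary and secondary tracker analyses: "only subjects who meet the minimum wear threshold will be included in the analysis". The threshold has two joint parts: at least 3 valid days at baseline, and "a minimum of 3 valid days within each post-baseline 7-day period". A valid day has at least 20 hours of wear. Under SAP 7.4.7.1 the third period is Days 15 to 20, so it has six days. Neither document says that only the deficient week is set to missing.

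Other parts of the plan point elsewhere:

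- SAP 8.2.5.1 justifies using no imputation by the mixed model: "This analysis uses the available data to provide information about the unobserved data".
- SAP 6.1 states: "The mITT population will be used for all efficacy analysis". The mITT is defined by eligibility, product use and questionnaire data, not by wear.
- Protocol 13.3.1 has no wear filter; the Week 1 average "will be calculated over all non-missing days between study day 1 (product usage) through 7, inclusive".
- SAP 3.5 records one departure from the protocol, the mITT definition: "This has been updated in the SAP to include that subjects must meet the inclusion/exclusion criteria". The wear filter is not listed.
- SAP 10.3 lists membership of the analysis sets, "including the primary reason for exclusion from the SAF and mITT", but does not mention exclusions by the wear rule.

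**The concern.** Two kinds of subject leave the tracker analysis entirely. The first exits early. Protocol 9.2.2 lets subjects stop the gel when pain subsides, Protocol 9.2.3 ends their study the day after last treatment, and SAP 7.4.1 has a disposition code for leaving because pain is gone. The second stays to Day 21 but has too little wear in one week.

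Removing both makes the primary analysis one of wear-compliant completers, selected on events after baseline. Losing subjects whose pain resolved would tend to understate the MVPA change. Losing those who left for lack of efficacy would tend to overstate it. The same filter applies to all seven tested tracker variables: MVPA, steps, sedentary ratio, cadence, gait speed, and activity at 30 and 60 minutes after waking. The diary endpoints (NRS, WOMAC, Karolinska, EQ-5D-5L) are not affected.

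**Working it through.** **The plan's own sample size.** Inputs from Protocol 13.1 are two-sided alpha 0.05, power 80%, effect 0.25, a Wilcoxon signed rank test and 25% dropout. The paired-test size is ((1.960 + 0.842)/0.25)² = 125.6, or 128 by exact t. Dividing by the minimum Wilcoxon relative efficiency of 0.864 gives 145.3 or 148.1, close to the stated 147. Enrolment is 147/0.75 = 196, against 195 stated. The sample size is not in dispute; 147 is used below as a base.

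**Which stopping days fail.** Let d be the day of last use, with exit on d + 1 and the exit day not valid. Week 1 needs d ≥ 3, Week 2 (from Day 8) d ≥ 10, and the third period (from Day 15) d ≥ 17. So d = 1 to 16 fails the rule, and for d = 3 to 16 at least one valid week is discarded. If the exit day does count as valid, the ranges are 1 to 15 and 2 to 15. This shows which days matter, not how many subjects stop then.

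**One-week non-wear.** The weekly failure probability q is not in the documents. It is assumed here, and assumed independent across weeks. Share of subjects removed = 1 − (1 − q)³. Valid subject-weeks discarded = 441 × [(1 − q) − (1 − q)³], where 441 = 3 × 147.

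| q | Subjects removed | Of 147 | Kept, current rule | Kept per week, weekly rule | Valid weeks discarded |
|---|---|---|---|---|---|
| 2% | 5.9% | 9 | 138 | 144 | 17 |
| 5% | 14.3% | 21 | 126 | 140 | 41 |
| 10% | 27.1% | 40 | 107 | 132 | 75 |

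Power for a single week's comparison at effect 0.25 (efficiency 0.864), current rule against weekly rule, is 77% against 79%, 73% against 78%, and 66% against 75%.

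**Scattered missed days cost little.** If each day is valid independently with probability 80%, the chance of at least 3 valid days is 0.9953 for a seven-day week and 0.9830 for the six-day period. Then 0.9953² × 0.9830 = 97.4% of subjects pass. At 70% of days valid, 87.7% pass; at 60%, 67.0%.

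**Bias, for one mechanism.** Suppose a share p exits after Week 1 and the latent exit propensity has correlation r with the Week 1 change. Deleting those subjects shifts the Week 1 mean by r × φ(z)/(1 − p) SD, where z is the normal quantile at 1 − p.

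- p = 5%, r = 0.1: 0.011 SD.
- p = 20%, r = 0.3: 0.105 SD.
- If r is instead the correlation with the exit indicator, r × √(p/(1 − p)) gives 0.023 and 0.150 SD.
- At p = 20% and r = 0.3, the shift is −0.105 SD if all who exit are improvers, −0.049 if 75% are, 0 at half and half, and +0.105 if none are.

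**Does a weekly rule help?** A simulation with 195 subjects, 4000 runs, p = 20%, r = 0.3 and within-subject correlation 0.5 or 0.8 gave these biases:

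- Whole-subject exclusion: −0.103 to −0.107 SD in Week 1.
- Weekly rule, Week 1: within 0.002 SD.
- Weekly rule, Weeks 2 and 3, when exit depends on the observed Week 1 change: within 0.002 SD.
- Weekly rule, Weeks 2 and 3, when exit relates equally to all weeks: −0.057 to −0.058 SD remains at correlation 0.5 and −0.022 at 0.8, against −0.104 to −0.109 under whole-subject exclusion.

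**The case against.** Several points on the other side have weight.

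- **Early exit is not settled.** Protocol 8.1 keeps subjects who stop the gel, including for lack of efficacy, in the study for the remaining assessments. This conflicts with Protocol 9.2.3, and SAP 7.4.1 still codes lack of efficacy as a reason for discontinuation. The number of early exits cannot be known. The route through resolved pain is nevertheless supported by Protocol 9.2.2 and 9.2.3, and the one-week non-wear route needs neither section.
- **The threshold is lenient and the rates are assumed.** Both are true. Scattered non-wear matters little, and clustering of failures within subjects narrows the gap between the two rules. Harm needs early exit or whole weeks of low wear.
- **The available-data rationale is not defeated everywhere.** It holds for the diary endpoints. Gait and post-wake variables can be missing despite adequate wear, so some partial profiles may remain there. The criticism fits MVPA, the primary endpoint, best.
- **The document conflicts are partly a matter of record.** The protocol leaves detail to the SAP, device compliance is summarised, and the table shells are in a separate document. It cannot be shown that wear exclusions will go unreported. The omission from SAP 3.5 remains a gap.
- **A common set is defensible.** It keeps the same subjects in every week, matches sizing on completers, and suits the non-parametric fallback. That supports keeping it as a sensitivity analysis, but it does not answer selection on post-baseline events in the primary one. The 25% dropout allowance answers power, not selection.

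**Conclusion.** The point holds. Followed as written, SAP 8.2 discards validly observed weeks and selects the primary analysis set on later exit or non-wear. This is at odds with SAP 8.2.5.1 for MVPA and with the mITT statement in SAP 6.1. It should be corrected, but the harm is not established. The net direction is unknown and may be zero. The larger losses rest on assumed independent weekly failure. The top of the main bias range needs 20% of subjects to exit after Week 1, all in one direction; for scale, the design effect is 0.25 SD. Confidence is medium, because the sponsor may have intended a weekly rule without writing it.

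**What to change.** In SAP 8.2, make the week the unit: a post-baseline week enters the MMRM if the baseline period and that week each have at least 3 valid 20-hour days. The same sentence should say whether a qualifying week averages only valid days or all non-missing days, which the current text leaves open. Report the all-weeks-valid set as a sensitivity analysis, with the numbers of subjects and weeks the rule removes, and list the wear rule in SAP 3.5.

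SAP 8.2.2 says: "If data are found to be non-normal, the Friedman Test will be used". That test needs complete weeks, so add that it uses the all-weeks-valid subset.

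The cost is a few sentences and one sensitivity analysis on data already collected, plus reprogramming of double-programmed outputs for seven variables. SAP version 2.0 already reflects the data review meeting, so the change should be dated before database lock. If tracker results have been seen, keep the current set as primary and report the weekly rule as the sensitivity analysis. The downsides are unequal numbers of weeks per subject, and Weeks 2 and 3 that are fully protected only if exit depends on observed data. Aligning Protocol 9.2.3 with 8.1, so that wear continues to Day 21 after the gel is stopped, would help only if data collection is still open, and is probably moot.
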